Study treatment should be administered by the patient once per day. Patients will return to the site every 2 weeks until Week 4 (V4) and then every 4 weeks for study medication and study assessments as specified in -[Table 7-1](#) and [Table 7-2](#).

Serious adverse events, regardless of causality, occurring after the subject has provided consent until 30 days following the last administration of study treatment must be reported to the Novartis drug safety team within 24 hours of the investigator learning of its occurrence.

Patients who discontinue study treatment early before completing the study (regardless if the discontinuation occurs at core or extension phase) should be scheduled for a visit as soon as possible, at which time all of the assessments listed for SEC (visit 777) must be performed.

Figure 4-1 Study design

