7.1.2 Treatment period

The duration of core phase treatment is 48 weeks. Patient visits will occur every 2 weeks during the first month of treatment and then every 4 weeks thereafter until Visit 777 (SEC).

Having completed the screening period (including the 5-day wash out period for patients previously treated with deferiprone (DFO) or deferoxamine (DFP)), patients who are eligible will be enrolled to receive deferasirox DT during 24 weeks then switch to deferasirox FCT for 24 weeks. Daily dose is calculated by the physician based on the patient's actual body weight.

At the start of treatment, iron chelation naïve patients will receive deferasirox DT 10 mg/kg (NTDT patients) or 20 mg/kg (TDT patients) once daily then will transition to the equivalent FCT dose as outlined in the following table.

Table 7-3 Equivalent dose to be used: Deferasirox DT vs Deferasirox FCT

Equivalent dose to be used	
Deferasirox DT (mg/kg/day)	Deferasirox FCT (mg/kg/day)
5	3.5
10	7
15	10.5
20	14
25	17.5
30	21
35	24.5
40	28

All iron chelation pre-treated patients will follow the below guidance:

Patients who were taking deferoxamine (DFO), will need to take the deferasirox DT equivalent deferasirox. For deferiprone (DFP) the dose of deferasirox DT will be based on their serum ferritin. Please refer to [Table 6-2](#).

At the Week 48 visit, patients will roll over to the extension phase in the case that none of the End of Study criteria is met at that time. The patient will receive deferasirox FCT following the same dose regulations and adjustments as per the core phase.

The treatment period of the extension study is approximately 52 weeks (including treatment period (48 weeks), Study Evaluation Completion and 4 weeks Safety Follow-up visits)

For details on study design and dose adjustments, see [Section 4](#) and [Section 6.3](#).

For details of assessments, see [Table 7-1](#) and [Table 7-2](#).

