7.2.2.6.2 Clinical chemistry

Clinical chemistry samples will be collected as described in [Table 7-1](#) and [Table 7-2](#) following local standard practice.

Parameters to be measured will include: albumin, alkaline phosphatase, ALT (SGPT), AST (SGOT), bicarbonate, calcium, chloride, serum creatinine, creatine kinase, glucose, inorganic phosphorus, potassium, sodium, total bilirubin (direct and indirect bilirubin only required if total bilirubin is > 1.5 ULN) total cholesterol, LDL, HDL, lactate dehydrogenase (LDH), total protein, triglycerides, blood urea nitrogen (BUN) or urea, uric acid, C-reactive protein (CRP).

In addition, serum creatinine will be measured every 2 weeks during the first four weeks after first study drug administration and then monthly. Refer to [Table 7-1](#) and [Table 7-2](#) for specifics.

Creatinine clearance will be estimated using the Cockcroft-Gault equation for adult patients and Schwartz formula for pediatric patients. This estimate will be provided each time serum creatinine is collected. The formula should be consistently used throughout the study for a particular patient.

Use the following reference source for calculation of creatinine clearance:

- <https://reference.medscape.com/calculator/creatinine-clearance-cockcroft-gault>
- <http://wwwusers.med.cornell.edu/~spon/picu/calc/crclsch2.htm>

Serum ferritin test will also be performed at the screening visit to assess the eligibility of the patient. Serum ferritin testing will also be performed as described on [Table 7-1](#) and [Table 7-2](#).

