10.5.3.3 Laboratory abnormalities

The summary of laboratory evaluations will be presented for different groups of laboratory tests (hematology, serum chemistry, serum ferritin, serum creatinine, and urinalysis). Descriptive summary statistics for the change from baseline to each study visit will be presented. These descriptive summaries will be presented by test group, laboratory test and treatment group. Change from baseline will only be summarized for patients with both baseline and post-baseline. The laboratory evaluations will be summarized separately and compared for two treatment groups FCT (Week 25 to 48) and DT (Baseline Day 1 to Week 24).

For each parameter, the maximum change from baseline within each study period will be evaluated analogously.

In addition, shift tables will be provided for all parameters to compare a patient's baseline laboratory evaluation relative to the visit's observed value. For the shift tables, the normal laboratory ranges will be used to evaluate whether a particular laboratory test value was normal, low, or high for each visit value relative to whether or not the baseline value was normal, low, or high. These summaries will be presented by laboratory test and treatment group. Shifts will be presented by visit as well as for most extreme values post-baseline.

Grading of laboratory values will be assigned programmatically as per NCI Common Terminology Criteria for Adverse Events (CTCAE) version 4.3. The calculation of CTCAE grades will be based on the observed laboratory values only, clinical assessments will not be taken into account.

CTCAE Grade 0 will be assigned for all non-missing values not graded as 1 or higher. Grade 5 will not be used.

For laboratory tests where grades are not defined by CTCAE v4.3, results will be categorized as low/normal/high based on laboratory normal ranges.

The following summaries will be generated separately for hematology, and biochemistry tests:

- Listing of all laboratory data with values flagged to show the corresponding CTCAE v4.3 grades if applicable and the classifications relative to the laboratory normal ranges ([Table 10-1](#))
- For laboratory tests where grades are defined by CTCAE v4.3
- Worst post-baseline CTCAE grade (regardless of the baseline status). Each patient will be counted only once for the worst grade observed post-baseline.
- Shift tables using CTCAE v4.3 grades to compare baseline to the worst on-treatment value

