### **Visit window**

Visit wise following window period will be used:

Visit 3 Date of visit should be 14 days from Visit 2 also consider buffer +/-2 days (e.g. Timeframe to do the visit is 12 days to 16 days)

Visit 4 Date of visit should be 28 days from Visit 2 also consider buffer +/-2 days (e.g. Timeframe to do the visit is 26 days to 30 days)

Visit 5 Date of visit should be 56 days from Visit 2 also consider buffer +/-2 days (e.g. Timeframe to do the visit is 54 days to 58 days)

Visit 6 Date of visit should be 84 days from Visit 2 also consider buffer +/-2 days (e.g. Timeframe to do the visit is 82 days to 86 days)

Visit 7 Date of visit should be 112 days from Visit 2 also consider buffer +/-2 days (e.g. Timeframe to do the visit is 110 days to 114 days)

Visit 8 Date of visit should be 140 days from Visit 2 also consider buffer +/-7 days (e.g. Timeframe to do the visit is 133 days to 147 days)

Visit 9 Date of visit should be 168 days from Visit 2 also consider buffer +/-7 days (e.g. Timeframe to do the visit is 161 days to 175 days)

Visit 10 Date of visit should be 196 days from Visit 2 also consider buffer +/-7 days (e.g. Timeframe to do the visit is 189 days to 203 days)

Visit 11 Date of visit should be 224 days from Visit 2 also consider buffer +/-7 days (e.g. Timeframe to do the visit is 217 days to 231 days)

Visit 12 Date of visit should be 252 days from Visit 2 also consider buffer +/-7 days (e.g. Timeframe to do the visit is 245 days to 259 days)

Visit 13 Date of visit should be 280 days from Visit 2 also consider buffer +/-7 days (e.g. Timeframe to do the visit is 273 days to 287 days)

Visit 14 Date of visit should be 308 days from Visit 2 also consider buffer +/-7 days (e.g. Timeframe to do the visit is 301 days to 315 days)

Visit 15 Date of visit should be 336 days from Visit 2 also consider buffer +/-7 days (e.g. Timeframe to do the visit is 329 days to 343 days)

Visit 16 Date of visit should be 364 days from Visit 2 also consider buffer +/-7 days (e.g. Timeframe to do the visit is 357 days to 371 days)

Visit 17 Date of visit should be 392 days from Visit 2 also consider buffer +/-7 days (e.g. Timeframe to do the visit is 385 days to 399 days)

Visit 18 Date of visit should be 420 days from Visit 2 also consider buffer +/-7 days (e.g. Timeframe to do the visit is 413 days to 427 days)

Visit 19 Date of visit should be 448 days from Visit 2 also consider buffer +/-7 days (e.g. Timeframe to do the visit is 441 days to 455 days)

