## 2.8.3 Laboratory data

The summary of laboratory evaluations will be presented for different groups of laboratory tests (hematology, serum chemistry, serum ferritin, serum creatinine, and urinalysis) for different treatment periods (core and extension). Descriptive summary statistics for the change from baseline to each study visit will be presented. These descriptive summaries will be presented by test group, laboratory test and treatment group. Change from baseline will be summarized only for the patients who have both baseline and post-baseline assessment. For each parameter, maximum change from baseline within each study period will be evaluated analogously.

In addition, shift tables will be provided for all parameters to compare a patient's baseline laboratory evaluation relative to the visit's observed value. For the shift tables, the normal laboratory ranges will be used to evaluate whether a particular laboratory test value was normal, low, or high for each visit value relative to whether or not the baseline value was normal, low, or high. These summaries will be presented by laboratory test and treatment group. Shifts will be presented by visit as well as for most extreme values post-baseline.

Grading of laboratory values will be assigned programmatically as per NCI Common Terminology Criteria for Adverse Events (CTCAE). The calculation of CTCAE grades will be based on the observed laboratory values only, clinical assessments will not be taken into account.

CTCAE Grade 0 will be assigned for all non-missing values not graded as 1 or higher. Grade 5 will not be used.

For laboratory tests where grades are not defined by CTCAE, results will be categorized as low/normal/high based on laboratory normal ranges.

The following summaries will be generated separately for hematology and biochemistry tests:

- Reporting of all laboratory data with values flagged to show the corresponding CTCAE grades if applicable and the classifications relative to the laboratory normal ranges ([Table 5.3.1](#))

For laboratory tests where grades are defined by CTCAE

- Worst post-baseline CTCAE grade (regardless of the baseline status). Each patient will be counted only once for the worst grade observed post-baseline.
- Shift tables using CTCAE v4.3 grades to compare baseline to the worst on-treatment value

For laboratory tests where grades are not defined by CTCAE

- Shift tables using the low/normal/high/ (low and high)

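### Seven scheduled laboratory visits on DT against six on FCT: a by-formulation comparison of worst values is modestly biased against DT, other things equal

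*Protocol*

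**What the plan says.** **Schedule.** Protocol 4.1: "Patients will return to the site every 2 weeks until Week 4 (V4) and then every 4 weeks". Protocol 7.2.2.6.2 repeats this for one test: "serum creatinine will be measured every 2 weeks during the first four weeks after first study drug administration and then monthly". Table 7-1 marks hematology, biochemistry, creatinine and urine tests at every visit, Week 2 included. The SAP visit windows carry the same early visit ("Visit 3 Date of visit should be 14 days from Visit 2"). They then go from Visit 9 (day 168, Week 24) straight to Visit 10 (day 196, Week 28), so no two-week visit follows the change to FCT.

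**Comparison.** Laboratory change on FCT (Week 25 to 48) against DT (Day 1 to Week 24) is part of a secondary endpoint (Protocol Table 3-1, SAP Table 1.2.1). Protocol 10.5.3.3 says: "The laboratory evaluations will be summarized separately and compared for two treatment groups FCT (Week 25 to 48", with DT (Day 1 to Week 24) as the other group. The next paragraph adds: "For each parameter, the maximum change from baseline within each study period will be evaluated analogously". Shifts for the most extreme post-baseline values follow, and both documents list this item: "Worst post-baseline CTCAE grade (regardless of the baseline status".

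**Where the wording is looser.** SAP 2.8.3 leaves out the sentence about comparing the two formulations and describes its summaries as "for different treatment periods (core and extension", before it too refers to each study period. It still presents results by treatment group, which SAP 2.1 defines as DT and FCT. Neither document limits the extreme-value summaries to matched visits.

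**The concern.** A maximum, or the worst of several grades, tends to grow with the number of values it is taken from. If worst values are tabulated by formulation, DT has seven scheduled chances and FCT six. With identical laboratory behaviour on both formulations, DT would then be expected to show somewhat more worst-grade abnormalities and slightly larger maximum changes.

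Timing differs too. A transient change two weeks after starting treatment can be recorded on DT. On FCT the first scheduled sample is at Week 28. At stake is the reading of a descriptive safety comparison between the two formulations.

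**Working it through.** The plan gives no figure for this comparison, so there is none to reproduce.

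**Inputs**
- DT visits after baseline (Table 7-1): W2, W4, W8, W12, W16, W20, W24, so *k* = 7.
- FCT visits: W28, W32, W36, W40, W44, W48, so *k* = 6.
- Per-visit abnormality rate *p* and within-patient correlation ρ: not in the documents. Assumed ranges: *p* = 1% to 10%, ρ = 0 to 0.9, with no true difference between formulations.

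**Maximum change.** For exchangeable normal values the expected maximum depends on *k* through √(1−ρ) × E[max of *k* standard normals]. That expectation is 1.352 for seven values and 1.267 for six, a gap of 0.085.
- ρ = 0: 0.085 SD
- ρ = 0.5: 0.085 × √0.5 = 0.060 SD
- ρ = 0.9: 0.085 × √0.1 = 0.027 SD

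The figure at 0.5 is the relevant one. Changes measured from one shared baseline have variance 2σ²(1−r) and covariance σ²(1−r), where r is the correlation of the raw values, so they correlate at 0.5 whatever r is. The unit is the SD of the change.

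**Any abnormal value.** For independent visits this is 1 − (1−p)^k. At *p* = 5%: 1 − 0.95^7 = 30.2% and 1 − 0.95^6 = 26.5%. For correlated visits a common normal factor was used: ∫ φ(u)[1 − Φ((c − √ρ·u)/√(1−ρ))^k] du, with c = Φ⁻¹(1−p).

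| p | ρ | DT (7) | FCT (6) | Gap, points |
|---|---|---|---|---|
| 1% | 0 | 6.8% | 5.9% | 0.9 |
| 1% | 0.5 | 5.2% | 4.6% | 0.6 |
| 1% | 0.9 | 2.5% | 2.4% | 0.1 |
| 5% | 0 | 30.2% | 26.5% | 3.7 |
| 5% | 0.5 | 20.3% | 18.6% | 1.7 |
| 5% | 0.9 | 10.5% | 10.0% | 0.5 |
| 10% | 0 | 52.2% | 46.9% | 5.3 |
| 10% | 0.5 | 34.5% | 32.1% | 2.5 |
| 10% | 0.9 | 18.9% | 18.2% | 0.7 |

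Gaps are taken before rounding. With exchangeable visits the relative excess cannot pass 7/6 = 1.167, and it shrinks as correlation rises: at *p* = 5% the ratio is 1.14, 1.09 and 1.05 for ρ = 0, 0.5 and 0.9.

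**Two-consecutive flags (Protocol Table 10-1).** There are six scheduled adjacent pairs on DT and five on FCT. W2 and W4 are 14 days apart, so they meet the 7-day rule. At *p* = 5% with independent visits, the chance of at least one abnormal pair is 1.43% against 1.20%.

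**After matching.** W4–W24 and W28–W48 each give six values at four-week spacing, and the part of the difference due to visit count becomes zero.

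**The case against.** A reader might infer that the plan makes DT look worse by construction. The documents do not support that, for two reasons.

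First, a by-formulation worst-value table is inferred rather than spelled out. The worst-grade item names no formulation period. The graded shift tables use the worst on-treatment value, and on-treatment is a single segment from first dose to 30 days after last dose, covering both formulations (Protocol 10.5.3.1, SAP 2.8). The SAP's periods can be read as core and extension. This stands as a point about wording. However, the secondary endpoint, the comparison sentence in Protocol 10.5.3.3 and the by-treatment-group presentation make the formulation reading the natural one.

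Second, other features act on the same comparison:
- On a Day 1 baseline, FCT change carries any drift from the DT period. SAP 2.8.3 may instead take the start of each period as baseline.
- Core completers who do not roll over have a completion visit with laboratory tests (Protocol 7.1, Table 7-2). If it is separate from Week 48, FCT also reaches seven.
- Patients who leave early on DT stay in the Safety Set with fewer than seven DT values.
- Early switchers (Protocol 4.2) move visits to FCT if analysed by treatment received.

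This stands in full: the net direction cannot be fixed from the documents. These features do not, however, cancel the unequal count by design.

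It is also fair to say that the by-visit change and shift tables do not depend on visit count, that unscheduled values are by default averaged into the scheduled visit (SAP 2.1), and that SAP 2.7.2 plans no formal testing of secondary endpoints. Finally, simply deleting Week 2 would drop real worst values, and could drop a patient flagged at Weeks 2 and 4. That objection is right, and it shapes the fix.

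**Conclusion.** The visit counts are unequal (seven against six) and nothing in either document matches them. Read by formulation, the extreme-value summaries are biased modestly against DT, other things equal. At correlation 0.5 the gap is about 0.06 SD in maximum change and, at an assumed 5% rate, about 1.7 points in any-abnormal rates. Across the assumed range the any-abnormal gap runs from about 0.1 to 5 points.

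These sizes assume full attendance, exchangeable visits and no true difference. They do not describe a change concentrated at Week 2, which the schedule would catch on DT only and for which the documents give no rate. They also do not establish which formulation the complete comparison would favour.

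This is a low-cost improvement to a descriptive safety comparison. The primary preference analysis and the sample size are untouched.

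**What to change.** In Protocol 10.5.3.3 and SAP 2.8.3:

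1. State that, for the DT–FCT laboratory comparison, study period means the DT period and the FCT period.
2. Base the DT–FCT comparison of worst grade, most extreme value and maximum change on the matched four-weekly visits: W4, W8, W12, W16, W20, W24 against W28, W32, W36, W40, W44, W48. This also leaves out a separate completion-visit sample.
3. Keep the all-data worst-value tables, the two-consecutive flags and the listings, with Week 2 and unscheduled values included. Add a footnote that DT has one extra scheduled sample.

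The cost is a short SAP text change, a visit filter and one extra set of descriptive tables. The downside is that the Week 2 value does not count in the matched comparison, although it is still reported everywhere else. Matching does not deal with baseline choice, switching or early withdrawal, which need their own statement.

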10.5.3.4 Other safety data

Data from vital signs, body weight, ECG, ocular, and auditory examinations will be listed and summarized with descriptive statistics as appropriate separately for the Safety Set. All new or worsened abnormalities will be recorded on the AE eCRF page.

ECG

ECG will be performed at baseline and EOT. Abnormalities will be reported together with an overall interpretation of the findings. Any abnormalities at baseline will be summarized. At EOT, the investigator will flag all abnormalities which are new or worsened since baseline. All new or worsened abnormalities will be recorded on the AE eCRF page. All findings of patients with new or worsened clinically significant abnormalities will be listed.

Vital signs

Measurements of vital signs and body weight done more than 30 days after discontinuation of study medication, will be excluded from the analysis but will be listed.

The change from baseline in diastolic blood pressure, systolic blood pressure, pulse rate, and weight will be summarized by scheduled visit with n, mean, SD, minimum, median, and maximum values.

A listing will be provided for all vital signs and weight. Notable vital signs and weight values are flagged. The criteria for notably abnormal vital signs and weight are displayed in [Table 10-2](#).

[figure not shown]

Table 10-2 Definition of notable ranges for vital signs and weight

Systolic blood pressure	≥180 mmHg / ≤90 mmHg with increase / decrease from baseline of ≥20 mmHg
Diastolic blood pressure	≥105 mmHg / ≤50 mmHg with increase / decrease from baseline of ≥15 mmHg
Pulse rate	≥120 bpm / ≤50 bpm with increase / decrease from baseline of ≥15 bpm
Weight	≥7% increase or decrease from baseline weight

Auditory, chest x-ray and ocular assessment evaluations

Auditory evaluations, chest x-ray and ocular examinations will be performed at baseline and at 12 months visit. Any abnormalities at baseline will be summarized. Abnormalities will be reported together with an overall interpretation of the findings. All new or worsened abnormalities will be recorded on the AE eCRF page. All findings of patients with new or worsened clinically significant abnormalities will be listed.

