4.1 Description of study design

This is an open-label, multicenter, single arm, phase II study aimed at collecting data on preference for iron chelation therapy in patients with transfusion-dependent thalassemia (TDT) or non-transfusion-dependent thalassemia (NTDT) throughout a 48 week treatment period.

It is a pre-requisite for the patient to provide written consent for participation in this study. This must be in place prior to performing any study-related procedures or assessments, including those described at the screening visit (please refer to [Table 7-1](#) and [Table 7-2](#)

Patients will undergo up to 4 weeks of screening and if deemed eligible, will receive deferasirox dispersible tablet (DT) formulation for 24 weeks. At the completion of 24 weeks patients will be transitioned on Week 25 to an equivalent dose of the deferasirox film coated tablet (FCT) formulation and continue treatment until Week 48 (EOT of Core Phase).

Patients can then continue deferasirox FCT formulation as per the judgment of the investigator, through an extension phase for a maximum of 12 months from the last dose of deferasirox FCT received at the end of period 2 in the Core Phase.

If one of the end of study criterion is met at any time during the study, the patient must discontinue from the study and should complete the Study Evaluation Completion (SEC - visit number 777). Please refer to [Section 4.4](#) .

Patients must be followed up for 30 days after the last dose of study drug for safety evaluation (safety follow up visit).

- Core Phase:
 - Screening phase which lasts for a maximum of 4 weeks to determine patient eligibility followed by
 - Baseline visit (day 1)
 - Period 1: deferasirox DT as 20-40 mg/kg/day dose regimen of dispersible tablet formulation for 24 weeks followed by
 - Period 2: deferasirox FCT as 14-28 mg/kg/day dose regimen of film- coated tablet for 24 weeks.
- Extension Phase:

Deferasirox FCT as 14-28 mg/kg/day dose regimen of film-coated tablet.
- PRO Validation Sub-study:
 - Patients in Egypt and Thailand may participate in this optional sub-study [sub-study protocol will only be submitted in the participating countries]

[figure not shown]
Participation in the extension phase is optional. Please refer to [Section 4.4](#) for EOS criteria.

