7.2.2.5 Auditory and ocular examination

Patients will undergo auditory and ocular examinations at screening, Week 48 and at unscheduled visits (if needed). For specifications refer to [Table 7-1](#) and [Table 7-2](#)

The auditory examination includes the following assessments:

- Comprehensive audiometry threshold examination
- Speech recognition

The ophthalmologic examination includes the following assessments:

- Visual acuity test
- Tonometry
- Slit lamp exam of anterior segment
- Slit lamp exam of the lens
- Funduscopy and retinal examination

Information about the audiometry and ocular examinations must be present in the source documentation at study site. Significant findings of the audiometry and ocular examinations that meet the definition of an AE must be recorded in the adverse event summary page of the case report form.

Please follow the guidance below for children aged 2 to 5. It can also be applied for children aged 5 to 7 who cannot complete the aforementioned ocular tests:

- Sedation is not requested nor required.
- The ophthalmologist of each site must decide what is age-appropriate ocular testing without the use of sedation. If any aspect of the ocular testing listed above cannot be completed, please document this in the CRF (which assessments and the reason).
- Once the site has determined which assessment can be performed for a given patient in the screening visit, then these assessments must be repeated consistently at subsequent visits
- It is critical to collect the visual acuity results. Please collect 'best corrected' visual acuity for all patients (for example: do with glasses if done with glasses before).
- The preferred method of collection for tonometry is applanation tonometry. If not possible, then do an age-appropriate procure (without sedation).

For children aged 2 to 5 and older who do not cooperate, speech audiometry should be performed. If not possible, then the speech recognition test will be suffice.

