10.5.3.2 Adverse events (AEs)

Summary tables for adverse events (AEs) will include only AEs that started or worsened during the on-treatment period, the *treatment-emergent* AEs. The AEs will be summarized separately and compared for two treatment groups FCT (Week 25 to 48) and DT (Baseline Day 1 to Week 24).

The incidence of treatment-emergent adverse events (new or worsening from baseline) will be summarized by system organ class and or preferred term, severity (based on mild, moderate, severe, life threatening, death), type of adverse event, relation to study treatment. If a patient reported more than one AE with the same preferred term, the AE with the greatest severity will be presented. If a patient reported more than one AE within the same primary system organ class, the patient will be counted only once with the greatest severity at the system organ class level, where applicable.

Serious adverse events, non-serious adverse events and adverse events of special interest (AESI) which are specific gastrointestinal events during the on-treatment period will be tabulated.

Separate summaries will be provided for death, SAE, other significant AEs leading to discontinuation and AEs leading to dose adjustment (including study treatment discontinuation).

As appropriate, the incidence of AEs will be presented per 100 patient years of exposure.

All AEs, deaths and serious adverse events (including those from the pre and post-treatment periods) will be listed and those collected during the pre-treatment and post-treatment period will be flagged.

A graphical display of relative frequencies within system organ classes and relative risks, as appropriate, may be presented is required.

For AEs of special interest, time-to-event analysis will be performed, as appropriate and as described in the statistical analysis plan. Results will be tabulated and the Kaplan-Meier estimates for the cumulative rate will be plotted.

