An overall summary of type of AEs (e.g. serious, leading to study drug discontinuation, requiring dose adjustment and/or interruption) will be presented by treatment (overall and severe). This summary as well as the incidence of AEs (overall and severe), regardless of study drug relationship, will additionally be provided separately for pediatric and adult patients. AEs will be summarized by presenting the number and percentage of patients having at least one AE, and having at least one AE by system organ class and/or preferred term, severity, and relation to study drug by treatment. A patient with multiple occurrences of an AE will be counted only once in the AE category.

All AEs, deaths and SAEs (including those from the pre and post-treatment periods) will be summarized and listed and those collected during the pre-treatment and post-treatment period will be flagged. Severity of AEs will be assessed as mild, moderate, or severe.

Separate summaries will be provided for deaths, SAEs, other significant AEs leading to discontinuation, and AEs leading to dose adjustment (including study treatment discontinuation).

A graphical display of relative frequencies within system organ classes and risks difference = risk in FCT-risk in DT (because if in DT, patient count for some SOC becomes 0, then relative risk will be undefined), as appropriate, may be presented by forest plot.

The following formula will be used:

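### Eye, hearing and ECG examinations are repeated on schedule only at Week 48, and no rule assigns findings first made then to a formulation, so the FCT-versus-DT adverse event comparison leans against FCT

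*Protocol*

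**What the plan says.** **Schedule.** Protocol 7.2.2.5: "Patients will undergo auditory and ocular examinations at screening, Week 48 and at unscheduled visits (if needed". Section 10.5.3.4 gives the same timing for the analysis: "Auditory evaluations, chest x-ray and ocular examinations will be performed at baseline and at 12 months visit". For the electrocardiogram it says "ECG will be performed at baseline and EOT". Section 4.1 places that point at Week 48 ("continue treatment until Week 48 (EOT of Core Phase"), and 7.2.2.7.1 lists screening and Week 48. Table 7-1 shows none of the three at Week 24, the last DT visit. Table 7-2 shows none at the Study Evaluation Completion visit, so a patient who stops during DT has no repeat in the tables.

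**Route into the AE data.** Section 10.5.3.4: "All new or worsened abnormalities will be recorded on the AE eCRF page". Sections 7.2.2.5 and 7.2.2.7.1 are narrower. They send to the AE page only significant eye and hearing findings that qualify as AEs, and new or worsened ECG findings that are clinically significant.

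**Comparison.** Protocol 10.5.3.2 has AEs "summarized separately and compared for two treatment groups FCT (Week 25 to 48) and DT (Baseline Day 1 to Week 24". SAP 2.8.1 produces the AE tables by treatment. It also allows a forest plot by system organ class of "risks difference = risk in FCT-risk in DT", with a normal-approximation 95% interval.

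**Separate summaries.** SAP 2.8.4 tabulates ECG status at baseline and Week 48, and the overall eye, ear and chest X-ray interpretation. No FCT-versus-DT contrast is specified for these.

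**The concern.** The safety of FCT compared with DT is a stated secondary objective (protocol Table 3-1, SAP Table 1.2.1). Protocol 6.2.1.7 names decreased hearing and lens opacities as disturbances reported with deferasirox, so the eye and ear classes are ones a reader will look at.

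The two periods do not have equal chances of detection. The Week 48 examination is compared with screening and so looks back over both formulations, but it takes place at the end of FCT. The DT period has no matching examination. For a change without symptoms, the examination date is the only date anyone has observed, and it lies in the FCT window. The summaries in SAP 2.8.4 do not take these findings out of the AE tables by treatment.

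For laboratory data, SAP 2.8.3 deals with the change of formulation by setting a baseline for each period. That cannot be done here, because no Week 24 examination is scheduled.

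**Working it through.** The documents state no figure for this point, so there is nothing to reproduce. The check is a trace of the rules followed by an illustration with the SAP's own formula.

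**Trace**
1. Scheduled examinations: screening and Week 48 (protocol Table 7-1, 7.2.2.5, 7.2.2.7.1).
2. Exposure covered by the Week 48 examination: 24 weeks of DT plus 24 weeks of FCT, so 24/48 = 50% on DT for a patient who follows the planned sequence.
3. AE timing: the investigator records a start date (protocol 8.1.1). Nothing says what date to give a finding first seen at Week 48.
4. Imputation: SAP 5.1.2 compares partial dates only with treatment start, not with the change from DT to FCT. A complete examination date needs no imputation.

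**Formula** (SAP 2.8.1)

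RD = p1 − p2, with p1 the FCT proportion and p2 the DT proportion; SE = √[p1(1−p1)/N1 + p2(1−p2)/N2]; interval RD ± 1.96 × SE.

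**Assumptions, none given by the documents:** risk is constant over 48 weeks, so the true difference is about zero, and only examination-detected findings are counted. N is 130 in each column, the Week 48 number from the sample size section and not a safety denominator; 145 is shown for range.

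*All k findings dated at Week 48, none on DT, N = 130*
- k = 3: p1 = 3/130 = 2.3%; interval −0.3 to 4.9.
- k = 4: p1 = 4/130 = 3.1%; SE = √(0.0308 × 0.9692/130) = 0.0151; interval 0.1 to 6.0.
- k = 8: p1 = 8/130 = 6.2%; SE = √(0.0615 × 0.9385/130) = 0.0211; interval 2.0 to 10.3. About 4 of the 8 would have arisen in each period.

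*Varying the share f dated to FCT.* With 48-week incidence q, p1 = f·q and p2 = (1−f)·q, so RD = (2f−1)·q. For q = 5% and f = 0.75: p1 = 3.75%, p2 = 1.25%, RD = 2.5 points.

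| q | f | RD (points) | Interval, N = 130 | Interval, N = 145 |
|---|---|---|---|---|
| 2% | 1.00 | +2.0 | −0.41 to 4.41 | −0.28 to 4.28 |
| 5% | 1.00 | +5.0 | 1.25 to 8.75 | 1.45 to 8.55 |
| 10% | 1.00 | +10.0 | 4.84 to 15.16 | 5.12 to 14.88 |
| 2% | 0.75 | +1.0 | −1.42 to 3.42 | −1.29 to 3.29 |
| 5% | 0.75 | +2.5 | −1.28 to 6.28 | −1.08 to 6.08 |
| 10% | 0.75 | +5.0 | −0.26 to 10.26 | 0.02 to 9.98 |

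At f = 0.50 the RD is 0 in every case. The spurious difference depends on f, which neither document fixes.

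**The case against.** A reader might infer that every abnormality found by scheduled examination is counted against FCT, so that the comparison shows an FCT excess by construction. The documents do not support that:
- Attribution follows the recorded start date, and an investigator may give an onset during DT, for example from symptoms.
- A partial date can be imputed to the day after treatment start, which falls in DT (SAP 5.1.2).
- Protocol 4.2 allows a switch from FCT to DT in Period 2, so some patients may be on DT at Week 48. The documents do not say whether their AEs follow the period or the formulation taken.
- DT is not without observation. The physical examination at every visit covers eyes, ears and heart (protocol 7.2.2.1), and unscheduled eye and hearing examinations are allowed.
- Sections 7.2.2.5 and 7.2.2.7.1 would admit fewer findings as AEs than 10.5.3.4.

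The consequence can also be overstated. The forest plot is optional. Each system organ class also contains symptomatic events from both periods. SAP 2.7.2 plans no formal testing of secondary endpoints, so an interval that excludes zero triggers no decision.

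These points limit the size and certainty of the bias. They do not remove it. A physical examination does not replace a slit lamp, an audiogram or an ECG. None of the provisions above tells the analyst where to put a silent finding first seen at Week 48. The AE tables by treatment, unlike the plot, are not optional.

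**Conclusion.** The concern holds in a limited form. Findings first detected at the scheduled Week 48 eye, hearing or ECG examination cannot be assigned reliably to DT or FCT. They will tend to fall in the FCT window, and the likely bias is against FCT.

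The size is not determined by the documents. If all such findings are dated at Week 48 and none on DT, with 130 per column, four are enough for the SAP interval to exclude zero when there is no true difference. If 75% are dated to FCT, the same-sized columns give intervals that include zero at all three incidences tried. With 145 per column the 10% case only just excludes it. If half are dated to each period there is no bias. These results rest on assumed incidence, even onset over 48 weeks, and assumed denominators.

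This is worth correcting because it affects a stated secondary comparison and the correction is cheap. It has no bearing on the primary preference analysis.

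**What to change.** In SAP 2.8.1 and 2.8.4, and protocol 10.5.3.2 and 10.5.3.4:

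1. Define a category of abnormalities first detected at the scheduled Week 48 ocular, auditory or ECG examination, with no earlier documented symptom or onset. Include a chest X-ray done at that visit; Table 7-1 marks chest X-ray as done only if clinically indicated.
2. Report this category for the core phase as a whole (DT then FCT). Keep it in the overall AE tables and listings, show it apart from the DT and FCT columns, and leave it out of the FCT-minus-DT risk difference.
3. Identify it by how the finding was detected, through a link to the examination record. Matching the AE start date to the visit date would catch unrelated events starting that day and miss findings given another onset date.
4. Keep AEs with their own onset date in the comparison.
5. Reconcile 10.5.3.4 with 7.2.2.5 and 7.2.2.7.1 on which findings become AEs.

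The cost is SAP and protocol wording plus a derived flag, with no added examination. The downside is that examination-detected findings get no formulation-specific estimate, including those that truly arose on FCT; the schedule cannot supply one anyway. The SAP's document history places the interim lock before its latest revision, and SAP 2.14 includes core-phase safety in that interim, so a change made now should be recorded as made after that lock.
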